## **8.9 IMMUNOGENICITY ASSESSMENTS**

Not applicable.

## **8.10 HEALTH ECONOMICS OR MEDICAL RESOURCE UTILIZATION AND HEALTH ECONOMICS**

Health economics are not evaluated in this study.

## **8.11 USE OF BIOLOGICAL SAMPLES AND DATA FOR FUTURE RESEARCH**

Future research may help further the understanding of disease and the development of new medicines. Reuse of coded data and biological samples (leftover and additional) will be limited to future scientific research conducted under a research plan for the purpose of diagnosing, preventing, or treating diseases ([Section 10.7.1](#) for specification related to China). The future research projects will be conducted under the Sponsor's and/or its affiliates' and/or, if applicable, the partner of the Sponsor which has licensed the study drug to the Sponsor or which is co-developing the study drug with the Sponsor's control, acting alone or in collaboration with

research partners such as universities, research institutions or industrial partners with whom the coded data may be shared.

Data and biological samples will be stored and used for future research only when consented to by participants (see [Section 10.1.3](#)) and, when applicable, further information on the future research has been provided to the study participant, unless prohibited by local laws or IRBs/IECs (in such case, consent for future use of data/sample will not be included in the local ICF). The conditions for reuse will be adapted locally with the appropriate language in the ICF.

In any case, a specific consent will be collected for the performance of genetic analyses on leftover and/or additional samples.

### **Data protection – Processing of coded clinical data**

The study participant will be provided with all mandatory details of the data processing in Section 2 of the core ICF.

The Sponsor adopts safeguards for protecting participant confidentiality and personal data (see [Section 10.1.4](#)).

### **Use of leftover samples and additional samples for future research**

Remaining leftover samples will be used only after the study ends, ie, end of study as defined in the study protocol, upon consent of the participant. Additional/extra samples can be collected and used during the study conduct at a given timepoint (eg, at randomization visit) as defined in the study protocol.

The study participant will be provided with all mandatory details of the use of the human biological samples (leftover and additional) in Section 2 of the Core ICF.

Study participant data will be stored for up to 25 years for regulatory purposes and future research. Biological samples for future use will be stored for up to 25 years after the end of the study. Any samples remaining at the end of retention period will be destroyed. If a participant requests destruction of his/her samples before the end of the retention period, the Investigator must notify the Sponsor (or its contract organization) in writing. In such case, samples will be destroyed, and related coded data will be anonymized unless otherwise required by applicable laws.

## 9 STATISTICAL CONSIDERATIONS

The statistical analysis plan (SAP) will be finalized prior to database lock, and it will include a more technical and detailed description of the statistical analyses described in this section.

### 9.1 POPULATIONS FOR ANALYSES

The following populations for analyses are defined.

**Table 6 - Populations for analyses**

Population	Description
Screened	All participants who signed the ICF.
Randomized	All participants from screened population who have been allocated to a randomized intervention by IWRs regardless of whether the intervention was received.
Intent-to-treat (ITT)	All randomized participants. Participants will be analyzed according to the intervention allocated by randomization.
Safety	All randomized participants who have taken at least 1 dose of study intervention, regardless of the amount of intervention administered. Participants will be analyzed according to the intervention they received.
Pharmacokinetic (PK)	All participants from the safety population with at least one post-baseline PK result with adequate documentation of dosing and sampling dates and times. Participants having received only placebo will not be part of the PK population. Participants will be analyzed according to the intervention they received.
Naive targeted Immunotherapy population (NTIP)	All randomized participants who have never received targeted immunotherapy for psoriasis. Participants will be analyzed according to the intervention allocated by randomization.
Experienced Targeted Immunotherapy population (ETIP)	All randomized participants who previously received targeted immunotherapy for psoriasis. Participants will be analyzed according to the intervention allocated by randomization.

Participants exposed to study intervention before or without being randomized will not be considered randomized and will not be included in any analysis population. The safety experience of these participants will be reported separately.

Randomized participants for whom it is unclear whether they took the study intervention will be considered as exposed and will be included in the safety population as randomized.

For any participant randomized more than once, only the data associated with the first randomization (except if the first randomization is done by error) will be used in any analysis population. The safety experience associated with any later randomization will be reported separately.

## 9.2 STATISTICAL ANALYSES

This section is a summary of the planned statistical analyses of the most important endpoints including primary and key secondary endpoints.

### 9.2.1 General considerations

The baseline value is defined as the last available value before the first dose of double-blind IMP. For participants randomized but not treated, the baseline value is defined as the last available value before randomization.

Unless otherwise specified, analyses will be performed by intervention group/dose level and overall, for baseline and demographics characteristics.

The observation period will be divided into 3 segments:

- The **pre-treatment period** is defined as the period up to first double-blind IMP administration.
- The **treatment-emergent period** is defined as the period from the first IMP administration to the last IMP administration +5 days. The treatment-emergent period includes the following 2 periods:
  - The **on-treatment period** is defined as the period from the first IMP administration to the last administration of the IMP +1 day.
  - The **residual treatment period** is defined as the period from the end of the on-treatment period to the end of the treatment-emergent period.
- The **post-treatment period** is defined as the period from the end of the treatment-emergent period.

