DAY	-28 to -11	1	15(±3)	29(±3)	57(±3)	85(±3)		113(±3)
WEEK	-4 to -1.5	0	2	4	8	12		16
Screening & Diagnostic tests								
Urine pregnancy test (WOCBP only) t		X		X	X	X		X
12-lead Triplett ECG u	X	X	X	X	X	X		X
Laboratory tests (include hematology- CBC with differential and liver chemistries- complete metabolic panel) v	X	X	X	X	X	X		X
Fasting lipids panel w		X		X		X		
Pharmacodynamics								

Procedure a	Screening period (up to 4 weeks and not less than 11 days before Day 1) b	Treatment period (12 weeks) c						Post-treatment period (4 weeks after last dose IMP)
		Baseline/ randomization					End of Treatment (EoT)	
VISIT	1	2	3	4	5	6		7
DAY	-28 to -11	1	15(±3)	29(±3)	57(±3)	85(±3)		113(±3)
WEEK	-4 to -1.5	0	2	4	8	12		16
Pharmacokinetic (PK) Assessments								
SAR441566 PK			X y	X z	X aa	X z	X aa	
Safety								
AE, SAE, TEAE and AESI review		←-----→						
Concomitant medication review		←-----→						

a Participants who discontinue IMP treatment prior to completing the 12-week treatment period should be assessed as per the EoT visit at the earliest opportunity and no later than 7 days from the last dose of IMP. After the EoT visit: (a) Participants who accept to stay on study without IMP intake: all remaining visits described in the SoA should be performed until the EoS, but only clinical assessments, AE and concomitant medication review and patient reported outcomes should be carried out at the study visits. (b) Participants who withdraw consent from the study: should have an EoS visit 4 weeks after their last dose of IMP.

b The screening period may be extended to 6 weeks (+/- 3 days) if participants are awaiting consultation with a specialist to rule out or treat active TB infection, or approval from Sponsor, according to [E 30](#).

c The morning IMP at visit days should be taken on site.

d Prior to randomization.

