Overall, SAR441566 showed consistent PK and PD characteristics which support advancement into further clinical studies in participants. Both QD and BID dosing without regard to food are deemed feasible considering SAR441566  $t_{1/2z}$  of approximately 20 to 30 hours, negligible food effect at 200 mg single dose. High target occupancy was observed across the investigated dose levels in the MAD study (100 mg QD, 100/200/300 mg BID). The published estimates of TNF $\alpha$  occupancy indicate >98% for marketed TNF $\alpha$  inhibiting biologics (13) at average steady state concentration of efficacious dose. The mean TNF $\alpha$  occupancy measured on Day 14 was ~95% for 100 mg QD and at pre-dose (trough level) and ~100% for all other time points assessed across the investigated dose range, ie, at 3 hours post-dose (~Cmax) for 100 mg QD, at pre-dose and 3 hours post-dose for 100 mg, 200 mg and 300 mg BID, respectively, which is in line with the exposure-occupancy relationship established by *in vitro* studies (see also IB Section 5.1.2.4). These results suggest that 100 mg to 400 mg total daily doses can be considered potential therapeutically relevant doses. 50 mg QD is considered a sub-therapeutic dose based on the target occupancy results of doses >100 mg.

In the POM study (PDY16918) in participants with mild to moderate psoriasis, serum IL-17A, IL-17F and IL-22 levels markedly declined following 4-week treatment of 200 mg BID SAR441566, in contrast to placebo. Notably, the biomarker decreases were in line with the observed clinical improvement in TLS score of 17.7% with 90% CI [4.98 to 30.49] at Week 4 compared to placebo. The adjusted mean % improvement of 19.4% with 90% CI [6.28 to 32.48] in PASI at Week 4 was consistent with the clinically relevant improvement in the TLS score. The results obtained in the proof-of-mechanism study support the initiation of Phase 2 dose ranging studies as part of the further clinical development of SAR441566.

In summary, the dose levels selected for the current study are expected to be safe and, based on the target occupancy data from the MAD study, as well as the efficacy and biomarker outcomes from the proof-of-mechanism study, to span a range of potential therapeutically relevant as well as subtherapeutic doses which will allow to explore the dose-response relationship and the determination of the optimal therapeutic dose for future large-scale studies.

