3 STATISTICAL ANALYSES

3.1 GENERAL CONSIDERATIONS

In general, continuous data will be summarized using the number of observations available, mean, standard deviation (SD), median, Q1, Q3, minimum, and maximum. Categorical and ordinal data will be summarized using the count and percentage of participants. The graphical plots will be presented for selected endpoints including primary, secondary and some exploratory endpoints.

The baseline value is defined as the last available value before the first dose of double-blind investigational medicinal product (IMP). For participants randomized but not treated, the baseline value is defined as the last available value before randomization.

Unless otherwise specified, analyses will be performed by intervention group/dose level (and overall for baseline and demographics characteristics).

Observation period

The observation period will be divided into 4 segments:

- The **pre-treatment period** is defined as the period up to first double-blind investigational IMP administration.
- The **treatment-emergent (TE) period** is defined as the period from the first IMP administration to the last IMP administration + 5 days. The treatment-emergent period includes the following 2 periods:
 - The **on-treatment period** is defined as the period from the first IMP administration to the last administration of the IMP + 1 day.
 - The **residual treatment period** is defined as the period from the end of the on-treatment period to the end of the treatment-emergent period.
- The **post-treatment period** is defined as the period from the end of the treatment-emergent period.

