For selected laboratory variables including hemoglobin, hematocrit, erythrocyte, platelets, leukocytes, neutrophils, lymphocytes, monocytes, glucose, cholesterol, triglycerides, sitting systolic blood pressure, sitting diastolic blood pressure, and sitting heart rate mean changes from baseline with the corresponding standard error will be plotted over time.

Analyses according to PCSA

Potentially clinically significant abnormality (PCSA) analyses will be performed based on the PCSA list currently in effect at Sanofi at the time of the database lock. For parameters for which no PCSA criteria are defined, similar analyses will be done using the normal range, if applicable.

Analyses according to PCSA will be performed based on the worst value during the treatment-emergent period, using all measurements (either local or central, either scheduled, nonscheduled or repeated).

For laboratory variables, vital signs and ECG variables above, the incidence of participants with at least one PCSA during the treatment-emergent period will be summarized regardless of the baseline level and according to the following baseline status categories:

- Normal/missing
- Abnormal according to PCSA criterion or criteria

In case of missing local assay methods, they will be considered similar as those used in central lab for the analysis of PCSA as soon as the laboratory parameters correspond to the PCSA reference table.

Even if the local and central specimen are different, they can be considered similar for the analysis of PCSA as soon as the laboratory parameters correspond to the PCSA reference table.

Additional analyses for drug-induced liver injury

The following additional analyses will be performed for drug-induced liver injury:

- Time to onset of the initial alanine aminotransferase (ALT) or aspartate aminotransferase (AST) elevation ($>3 \times \text{ULN}$) and total bilirubin elevation ($>2 \times \text{ULN}$) during the treatment-emergent period may be analyzed using Kaplan-Meier method.
- A graph of the distribution of peak values of ALT versus peak values of total bilirubin during the treatment-emergent period will be provided.

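### The treatment-emergent period ends 5 days after the last dose but the early end-of-treatment visit may fall up to 7 days after it, so labs, vital signs and ECGs from a day 6–7 visit miss the PCSA and liver analyses

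*Protocol*

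**What the plan says.** **Analysis windows.** Protocol 9.2.1 says the treatment-emergent period "is defined as the period from the first IMP administration to the last IMP administration +5 days". SAP 3.1 has the same rule: it "is defined as the period from the first IMP administration to the last IMP administration + 5 days". Inside it lies the on-treatment period, which in SAP 3.1 "is defined as the period from the first IMP administration to the last administration of the IMP + 1 day".

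**Visit timing.** Under Schedule of Activities footnote a, participants who stop IMP before completing 12 weeks "should be assessed as per the EoT visit at the earliest opportunity and no later than 7 days from the last dose of IMP". Protocol 7.1.1 gives the same limit. Both places then restrict later visits, for those who remain on study without IMP, to clinical assessments, adverse event and medication review, and patient-reported outcomes. Safety labs and ECGs are not on that list.

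**Where the windows are used.** SAP 3.6.3.1 states: "Analyses according to PCSA will be performed based on the worst value during the treatment-emergent period". Protocol 9.2.6.2 has the same rule and adds an abnormal-ECG incidence over the same period. The peak ALT versus peak bilirubin plot, and the optional time-to-onset analysis of ALT/AST and bilirubin elevation, also use treatment-emergent values only. The last and worst quantitative values use the on-treatment period.

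**The concern.** The visit meant to collect an early discontinuer's closing safety data may legitimately take place after the main safety window has closed. No section of either document assigns such a value back to the treatment-emergent period.

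The gap is selective. The Schedule of Activities has completers take a dose on site at Week 12, so their EoT data lie inside the window. Only early discontinuers are exposed, and protocol 7.1 lists serious adverse events and clinically relevant laboratory deviations among the reasons for stopping. Clinically significant laboratory, vital-sign and ECG changes are a named secondary safety endpoint. Protocol 2.3.1 reports four ALT-elevation events of special interest in the multiple-dose study, so the liver displays matter here.

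**Working it through.** Neither document derives the 5 days, so there is no stated figure to reproduce. The check compares the windows.

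**Inputs**
- End of treatment-emergent period: last dose + 5 days (protocol 9.2.1, SAP 3.1).
- End of on-treatment period: last dose + 1 day (same sections).
- Latest early EoT visit: last dose + 7 days (footnote a, protocol 7.1.1).
- Half-life: "approximately 20 to 30 hours" (protocol 4.3).
- Planned total: 207. Dropout: 10%, stated in SAP 4 for the NTIP power calculation.

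**Gaps**
- Treatment-emergent analyses: 7 − 5 = 2 days. EoT visits on days 6 and 7 fall outside.
- Last/worst on-treatment summaries: 7 − 1 = 6 days. EoT visits on days 2 to 7 fall outside.

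**Illustrative count.** Assume that a given percentage of all 207 stop early, that all attend an early EoT visit, and that visits are spread evenly over days 1–7. The share outside the treatment-emergent period is then 2/7, and the share outside the on-treatment period 6/7.

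| Early stop | n (rounded) | Outside PCSA (n × 2/7) | Outside last/worst (n × 6/7) |
|---|---|---|---|
| 5% | 10 | 2.9 | 8.6 |
| 10% | 21 | 6.0 | 18.0 |
| 15% | 31 | 8.9 | 26.6 |

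**Leverage of one missed value.** If the strata are pooled for safety, 200 mg BID has 24 + 18 = 42 participants, as do 200 mg QD and 100 mg QD. Placebo has 24 + 9 = 33, and 100 mg BID and 50 mg QD have 24 each. One missed PCSA moves an arm's incidence by 1/42 = 2.4 to 1/24 = 4.2 percentage points.

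**Half-lives**
- 5 × 20 h = 100 h = 4.2 days; 5 × 30 h = 150 h = 6.25 days.
- At 30 h, day 5 is 120/30 = 4 half-lives, leaving 2^(−4) = 6.25% of drug. Day 7 leaves 2^(−168/30) = 2.1%.
- At 20 h, day 5 leaves 2^(−120/20) = 1.6%.

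**The case against.** The strongest reply is that little is lost in practice.

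- **Other outputs keep the value.** SAP Table 8 assigns labs, vital signs and ECGs to visits by study day, with no stated treatment-emergent cut-off. A day 6–7 value may therefore still appear in by-visit summaries. The SAP's follow-up summary for liver abnormalities has a category for return to baseline status after the last dose. This stands: a reader might infer that the data leave the safety analysis altogether, and the documents do not support that.
- **Adverse events are not lost.** A reader might also infer that late visits understate treatment-emergent adverse events. They do not. Events are classified by when they developed, worsened or became serious, not by visit date. Incomplete onset dates default to treatment-emergent unless there is definitive contrary information (SAP 3.6.2). Events starting on days 6–7 are reported as post-treatment.
- **More samples may exist.** Protocol 7.1.1 has abnormal labs or ECGs rechecked, at the investigator's judgement, before permanent discontinuation is decided. Section 8.3.4 repeats clinically significant labs, Appendix 6 asks for frequent liver tests after IMP is stopped, and section 8 allows unscheduled safety samples. PCSA uses all of these if they fall inside the window, so the abnormality that led to stopping is normally captured. This narrows the loss but does not remove it, because follow-up samples on days 6–7 are excluded by the same cut-off.
- **Prompt visits.** Seven days is a ceiling and the visit is wanted as soon as possible, so an even spread probably overstates the count. The 10% is a planning dropout rate for one stratum, not an observed IMP-discontinuation rate, and some dropouts may never attend. Both points stand.
- **Half-life.** Five days lies within the 4.2 to 6.25 day range, and neither document requires the window to cover five half-lives. The half-life alone does not make the window wrong.

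**Conclusion.** The mismatch is real and identical in both documents. A protocol-compliant early EoT lab, vital sign or ECG on day 6 or 7 is excluded from PCSA incidence, abnormal-ECG incidence and the treatment-emergent liver displays. For participants who stay on study off IMP, no later scheduled lab or ECG replaces it. Those who withdraw consent are asked to attend an end-of-study visit 4 weeks after the last dose, which is also outside the period.

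The main exposure is narrow: a new abnormality or a later peak first seen at a late EoT visit. How many participants are affected cannot be known from the documents. About 3 to 9 is an illustration that rests on 5–15% of 207 stopping early, full attendance and an even spread over days 1–7. Prompt visits would make it smaller. The point should be settled before database lock, because the omission falls only on early discontinuers and costs little to correct.

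The last/worst on-treatment summaries have the wider gap, since EoT values from day 2 onward fall outside them.

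**What to change.** Choose one of two changes to the analysis rules. Neither alters visit timing or clinical management.

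1. In protocol 9.2.1 and SAP 3.1, end the treatment-emergent period at last IMP dose + 7 days. The gap becomes 7 − 7 = 0 days, and the period also covers five half-lives at the upper stated value (6.25 days).
2. Keep + 5 days, and state in SAP 3.1 and 3.6.3.1 that the early EoT assessment counts as treatment-emergent whenever it occurs within the permitted limit.

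With either choice, state how the early EoT assessment enters the last/worst on-treatment summaries. Option 1 alone leaves those stopping at last dose + 1 day.

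**Cost.** Option 1 changes one number in each document, but events on days 6–7 after the last dose become treatment-emergent for every participant, completers included. Option 2 needs a short rule and its programming, and leaves adverse event classification unchanged. If only the SAP is changed, the departure from the protocol should be recorded in SAP 3.9.

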### 9.2.2 Primary endpoint analyses

#### 9.2.2.1 *Definition of endpoint*

The primary endpoint is the response in PASI75, which is defined by proportion of participants with a 75% or greater PASI improvement from baseline at Week 12.

#### 9.2.2.2 *Main analytical approach*

The primary endpoint will be analyzed with the primary estimand defined according to the following attributes:

- Endpoint: Proportion of participants with a 75% or greater PASI score improvement from baseline at Week 12.
- Intervention condition: SAR441566 200 mg BID, 100 mg BID, 200 mg QD, 100 mg QD and 50 mg QD will be compared to placebo.
- Analysis population: NTIP population

- Intercurrent events:
  - The IMP discontinuation: It will be handled with the treatment policy strategy. The primary endpoint will be assessed based on all assessments irrespective of the IMP discontinuation.
  - Starting the selected concomitant medication which could have an impact on the efficacy of IMP: It will be handled with the composite variable strategy. For primary endpoint, participants who receive selected concomitant medications will be considered as non-responders for time points after the medication usage. For other participants, all available data including those collected during the off-treatment period will be used to determine the responder/non-responder status.
- Population-level summary: Difference in the percentage of participants achieving PASI75 response at Week 12 between each active arm and placebo. The Cochran-Mantel-Haenszel test will be used for the primary endpoint analysis. Multiplicity adjustment will be provided (See [Section 9.2.5](#)). Further details will be specified in the SAP.

Missing data will be imputed to non-responders when the response to PASI75 is missing.

